3. A battery monitoring system that ensures there is enough battery power to vent the balloon and turn off the device as the battery decreases to a low level. As the battery deceases to low levels, the device will save enough power to ensure total balloon venting and shut down.**OBJECTIVE:** To determine whether use of the Fist Assist[®] device facilitates vein dilation before AVF creation.

Hypotheses:

Use of the Fist Assist[®] before AVF creation will enhance superficial vein dilation, resulting in increased absolute vein diameters at three months when compared to baseline values.

SPECIFIC AIM:

To determine whether the use of the Fist Assist[®] device for 360 hours over 90 days by patients with advanced CKD prior to AVF surgery results in significant increases in cephalic vein diameters prior to AVF surgery.

SUBJECTS:

Population:

Inclusion criteria: Patients followed in the Nephrology Clinic who are expected to initiate HD will be approached for participation in the study. We will consider all patients with eGFR<30 mL/min.1.73m².³⁹ Patients will be assigned to treatment with the Fist Assist[®].

Exclusion criteria: Refusal/inability to give informed consent, inability to comply with trial requirements, arm infections, and skin disorders that require frequent medical attention. In addition, we will exclude patients with obvious scarring from IV drug use or previous phlebitis. Patients will be excluded if they have previous occluded arteriovenous grafts or fistulae, arterial aneurysms, or arm deep vein thrombosis or any previous vascular surgery on their non-dominant arm. Patients will be excluded they have limited cognitive ability. Patients will be excluded if they have any motor or sensory deficits in their upper arms.

Patients will have a preliminary evaluation of their cephalic vein, measured 5 cm proximal to the styloid process of the radius, and also at the antecubital fossa. Patients will be excluded if there are no detectable superficial veins of at least 1.0 mm diameter, and also if a superficial vein of more than 3.0 mm is present in this lower arm location.

LOCATION: The study will be conducted in the Ambulatory Care facilities at the University of Chicago Medical Center (UCMC).

METHODOLOGY:

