Medical History: Medical records of enrolled patients will be reviewed to collect: date of birth, height, weight, ethnicity, and medical history related to factors which may affect vascular health, including but not limited to: dialysis history, diabetes, hypertension, systemic lupus erythromatosis, coronary artery disease, peripheral vascular disease, medication history, and any other factors that contribute to vascular health.

Intervention: The Fist Assist[®] device will be assigned to each enrolled subject by randomization code. All subjects will be asked to use their assigned device twice daily, for two 2-hour sessions, once in the morning and once in the evening. Patients will apply the device to the non-dominant arm above the level of the elbow, and to keep a written log to record use, complications and any problems.

Blood Draws: 10 mL of blood will be obtained from patients being enrolled at the time of their next routine standard of care phlebotomy. These samples will be frozen for future assays of endothelial biomarkers of nitric oxide production and venous dilation, such as asymmetric dimethyl arginine (ADMA) and its metabolites.

Doppler: Patients will undergo examination of their cephalic veins in the Nephrology Clinic, using a portable vascular ultrasound device operated by a co-investigator trained by the UCMC Vascular Lab in this technique. The cephalic vein, a superficial vein originating in the wrist, is the most common vein used for AVF creation. In order to standardize these measurements, the diameter of the cephalic vein and vein wall thickness will be measured in both arms at: (a) 5 cm proximal to the styloid process of the radius, and (b) at the antecubital fossa. The diameter and thickness of the vein will be measured using a B-mode image acquired using a standard ultrasound machine with vascular probe going from outer walls per protocol. Patients will be seated with arms supported at the level of the heart on an exam table with in a room with a temperature of at least 20 degrees Celsius. A layer of at least 1 cm of gel will be applied locally to optimize the ultrasound image quality. Vascular Doppler measurements will be obtained on both arms at the time of consent (baseline), and at the conclusion of therapy. Measurements will be recorded.

Follow Up: Those who are subsequently able to undergo successful AVF creation will be followed clinically for up to 12 months.

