Protocol: Informed consent will be obtained by the co-investigators using a written consent form approved by the Institutional Review Board. After informed consent is obtained, patients will receive: physical examination of both forearms; and a vascular Doppler to determine cephalic vein diameters of the nondominant arm. A 10 mL blood sample will be drawn at the next routine phlebotomy.

Patients will be asked to apply the Fist Assist[®] to the upper half of the non-dominant arm. Patients will be asked to use the device twice daily for two 2-hour periods, and report any complications or problems, using a log (see log attached at end of References). Patients will have follow up examinations with measurement of cephalic vein diameter at three months after enrollment.

Outcomes: The primary outcome will be the difference in vein diameter before and after Fist Assist[®] use. Secondary outcomes include: whether or not an AVF was created (versus a synthetic graft or use of a central venous catheter), whether the

resultant vascular access matured sufficiently to be used for HD, and the subsequent exposure of patients to central venous catheters during their first year of HD.

DURATION OF STUDY: All subjects will be enrolled and treated for three months. The duration of the study including data analysis and statistical analysis is expected to be 6-9 months.

| Table 1. Timeline for Study | | | |
|-----------------------------|----------|---------|--|
| Measurement | Baseline | Post-Rx | |
| H&P | Х | | |
| Clinical | Х | Х | |
| examinations | | | |
| Blood sample | Х | Х | |
| Doppler | Х | Х | |

DATA MANAGEMENT: Study data will be collected and managed using REDCap electronic data capture tools hosted at The University of Chicago.

STATISTICAL ANALYSES: The primary outcome of interest will be the difference in the diameter of the cephalic vein between baseline (Pre) and 3 months (Post) in patients treated with the Fist Assist[®] device. Based on prior work, mean vein diameters at baseline are anticipated to be approximately 1.8 mm with a standard deviation of 0.5 mm,⁴⁴ and we anticipate that the standard deviation of the change in diameter is likely to be approximately 0.75 mm.

Effect =[(DsPost)-(DsPre)]

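### First-year catheter exposure is a secondary outcome for all patients, but later follow-up is stated only for those with a successful AVF, and a first HD year does not fit a 6-9 month study

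*Combined protocol and SAP*

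**What the plan says.** All references are to the combined protocol and SAP.

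- **METHODOLOGY, Outcomes.** The secondary outcomes include "whether or not an AVF was created (versus a synthetic graft or use of a central venous catheter"), whether the resulting access matured enough to be used, and "exposure of patients to central venous catheters during their first year of HD". None is limited to patients who receive an AVF.
- **METHODOLOGY, Protocol.** The one follow-up visit for everyone is this: "Patients will have follow up examinations with measurement of cephalic vein diameter at three months after enrollment". Table 1 has a baseline column and a post-treatment column and nothing later.
- **METHODOLOGY, Follow Up.** Later follow-up is conditional: "Those who are subsequently able to undergo successful AVF creation will be followed clinically for up to 12 months". The paragraph does not say when the 12 months begin or what makes a creation successful.
- **METHODOLOGY, Medical History.** Records are reviewed for "medical history related to factors which may affect vascular health, including but not limited to: dialysis history". Later capture of access type, HD start or catheter use is not mentioned.
- **SUBJECTS, Inclusion criteria.** "Patients followed in the Nephrology Clinic who are expected to initiate HD will be approached for participation in the study".
- **DURATION OF STUDY.** "All subjects will be enrolled and treated for three months". Then: "The duration of the study including data analysis and statistical analysis is expected to be 6-9 months".

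**The concern.** There are two separate mismatches.

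The first is who is followed. The access outcomes cover patients who end up with a graft or a catheter as well as those with an AVF, but the stated later follow-up covers only the last group. Membership of that group is itself determined after treatment. A catheter-exposure figure built on it would describe patients selected on a favourable post-treatment event, and a reader could take it as describing everyone enrolled.

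The second is for how long. An outcome defined over a year of HD, in patients who have not started HD at entry, needs more calendar time than the study is said to last.

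At stake is whether the secondary outcomes that link vein diameter to actual vascular access can be reported as worded. The three-month diameter comparison is not at stake.

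**Working it through.** **1. Who is covered**

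| Item needed | Patients with a successful AVF | Patients without one |
|---|---|---|
| AVF created, yes or no | Follow Up paragraph | Implied: staff must learn this for everyone to apply the Follow Up rule |
| Graft versus catheter | Not applicable to the access created | No follow-up or source stated |
| HD start date | Could be collected within the stated follow-up | No follow-up or source stated |
| Catheter exposure in HD | Could be collected within the stated follow-up, for as long as it runs | No follow-up or source stated |

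Because success is not defined, a patient whose AVF was created but judged unsuccessful may also fall in the right-hand column.

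**2. Whether the HD year fits**

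Inputs: treatment of 3 months and study length T of 6 to 9 months including analysis (DURATION OF STUDY); outcome window of 12 months of HD (Outcomes); HD starting at or after enrolment (Inclusion criteria). The documents give no HD start time, so the start month h is an assumption, shown over a range.

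The stated duration does suit the primary outcome. Three months of treatment leaves 6 - 3 = 3 to 9 - 3 = 6 months for recruitment and analysis.

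For the catheter outcome:

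- End of first HD year, in months from enrolment = h + 12.
- HD months seen by study close for the first patient enrolled = max(0, T - h). Analysis time is set to zero, so these are upper limits for each assumed h.

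| HD start h (assumed) | HD year ends | Beyond month 9 by | Beyond month 6 by | HD months seen, T = 6 | HD months seen, T = 9 |
|---|---|---|---|---|---|
| 0 (most favourable) | 12 | 3 | 6 | 6 of 12 | 9 of 12 |
| 3 (end of treatment) | 15 | 6 | 9 | 3 of 12 | 6 of 12 |
| 6 | 18 | 9 | 12 | 0 | 3 of 12 |
| 9 | 21 | 12 | 15 | 0 | 0 |

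Patients enrolled later have less time. Even in the first row, the best possible case is 9/12 = 75% of the HD year. So if data collection closes at month 6 to 9, the number of patients with a complete first HD year is 0 in every row. This needs no assumption about accrual.

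**3. Whether the AVF follow-up covers the HD year**

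If the 12 months run from AVF creation and HD starts k months after creation, at most 12 - k months of the HD year are covered. Since no start point is stated, full coverage is not assured even for patients with a successful AVF.

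**The case against.** **The 6-9 months may mean the primary phase.** It is an expectation, and it directly follows the sentence on three months of treatment. The Follow Up paragraph separately allows up to 12 months, and nothing says data collection stops at month 9. This stands as a possible reading, but the text refers to the study as a whole. A reader might infer that first-year exposure cannot be reported for any patient; that holds only if collection closes at 6-9 months. The coverage gap remains on either reading.

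**Clinic records may supply the data.** These are nephrology clinic patients and the record review is open-ended. A reader might infer that the data will be missing, and the documents do not show that. They show only that no source or window is stated, since the review is placed under baseline history.

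**The 12 months is a maximum.** Agreed: it is not breached by a shorter follow-up. The difficulty is the missing start point and the restriction to one group.

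**Catheter exposure would be understated.** A reader might infer this because those left out include patients who received a catheter. The documents do not support a direction. Entry requires eGFR below 30 and an expectation of HD, so patients without an AVF also include those who have not started HD and have no exposure during it. The background also says that patients whose AVF fails to mature have longer catheter exposure, so the followed group is not low-exposure by definition. The mix is not given.

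**These outcomes are secondary and no test is planned on them.** True, and it limits the weight of the point.

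**Conclusion.** The mismatch holds on the text. Access type and first-year catheter exposure are outcomes for patients in general, while stated follow-up after three months is limited to those with a successful AVF. AVF creation for all is implied; graft-versus-catheter detail, HD start and catheter exposure in the remainder have no stated follow-up or source. Catheter exposure collected as written would describe a group selected after treatment, with a bias whose sign and size the documents do not allow one to derive.

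A first HD year ends at least 12 months after enrolment, which is 3 to 6 months beyond the stated duration. If HD is assumed to start at the end of treatment it ends at month 15, which is 6 to 9 months beyond. If data collection closes at the stated duration, no patient has a complete year. This rests on HD starting at or after enrolment and on the 6-9 months applying to the whole study, as its wording says.

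The primary diameter outcome and the planned sample of 90 are unaffected. The Follow Up, Outcomes and DURATION OF STUDY text should be reconciled before the secondary outcomes are reported.

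**What to change.** **(a) Follow everyone.** Amend the Follow Up paragraph so that all enrolled patients, whether or not an AVF is created, are followed by medical-record review to a stated cut-off. Collect access type and date, HD start date and catheter-days, using outside dialysis and surgical records where available. State the denominators: all enrolled patients for AVF creation, and all who start HD for catheter exposure. For maturation, either use every access created, as the outcome is now worded, or say explicitly that it is narrowed to AVFs.

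**(b) Make the window and the duration agree**, by one of two routes:

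- State that 6-9 months applies to the primary analysis, and give a longer follow-up for the first-year-of-HD outcome.
- Restate the outcome as catheter-days per observed HD day up to a stated cut-off, reporting how many patients started HD and their observed HD time. Say that this describes early HD and is not a substitute for first-year exposure.

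Report these outcomes as descriptive, and keep the primary diameter result on its present schedule.

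**Cost.** A protocol amendment and chart-review effort, with no new visit or procedure. Outside records may be incomplete and may need added authorisation. The first route lengthens calendar time; the second gives up the full-year outcome. Under either, patients who do not start HD before the cut-off contribute no catheter data.

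### The single-arm pre-post primary cannot by itself support the causal objective, and no defined analysis uses the untreated-arm scans the plan schedules

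*Combined protocol and SAP*

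**What the plan says.** The Objective is to learn whether the "device facilitates vein dilation before AVF creation". The Specific Aim asks whether device use "results in significant increases in cephalic vein diameters prior to AVF surgery". Both are causal statements. The Hypotheses section is narrower and expects "increased absolute vein diameters at three months when compared to baseline values".

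Statistical Analyses sets the primary to match the hypothesis: "The primary outcome of interest will be the difference in the diameter of the cephalic vein between baseline (Pre) and 3 months (Post"), among device-treated patients. The effect is Post minus Pre. Table 2 sizes it by paired t-test with an SD of change of 0.75 mm, and 90 patients are planned.

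On a possible comparator, the plan says:

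- **Intervention (Methodology):** "Patients will apply the device to the non-dominant arm above the level of the elbow". The device is "assigned to each enrolled subject by randomization code", but only one treatment is described and every patient receives it.
- **Doppler (Methodology):** "Vascular Doppler measurements will be obtained on both arms at the time of consent (baseline), and at the conclusion of therapy".
- **Protocol (Methodology):** after consent, patients receive "a vascular Doppler to determine cephalic vein diameters of the nondominant arm". The other arm is not mentioned.
- **Secondary aim (Statistical Analyses):** proportions reaching 2.5 mm and 3.0 mm are to be compared with those among controls, who are never defined.

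**The concern.** A significant paired test shows that mean diameter differed between two visits three months apart. It does not show why. The Doppler section standardises posture, landmarks, gel and technique, but sets only a lower limit for room temperature. None of these steps removes background change over three months in patients with advanced kidney disease. Any such change is added directly to the estimated effect.

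The plan appears to collect what is needed to address this, because the untreated arm is to be scanned at both visits. If the comparison is not written down beforehand, it will be chosen after the data are seen. If the narrower description in the Protocol paragraph is followed instead, the untreated arm will have no baseline, and that cannot be recovered later.

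**Working it through.** **Inputs from the plan.** SD of change 0.75 mm; paired t-test, alpha 0.05; n = 90; smallest clinically meaningful effect 0.25 mm; SD of vein diameter 0.5 mm.

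**Assumed, not in the documents.** Background shift; pre-post correlation ρ in the untreated arm; SD of change in the untreated arm, s₂; between-arm correlation of changes, r; and 80 evaluable pairs as a reduced case.

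**1. Table 2.** The plan does not state sidedness. A two-sided paired t-test with the noncentral t distribution gives, for 80%/90% power, 73/97, 20/26, 10/13, 7/9, 6/7 and 5/5 for effects of 0.25 to 1.50 mm. The plan prints 73/97, 21/27, 11/14, 8/9, 6/7 and 5/6. These agree to within one patient, so the sizing is sound for the question it tests.

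**2. Smallest significant change.** t(0.975, 89) × 0.75/√90 = 1.987 × 0.0791 = 0.157 mm.

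**3. Ineffective device with background change.** The chance of a significant increase is P(T > 1.987), where T is noncentral t with 89 df and noncentrality shift × √90/0.75. The last column gives the chance when a true device effect of 0.25 mm is added to the same shift.

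| Assumed shift (mm) | No device effect | True effect 0.25 mm |
|---|---|---|
| −0.10 | 0.1% | 47% |
| −0.05 | 0.5% | 71% |
| 0 | 2.5% | 88% |
| 0.05 | 9.1% | 96% |
| 0.10 | 23.9% | 99% |
| 0.25 | 87.9% | >99% |

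Upward drift imitates a device effect; downward drift hides one.

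**4. Does the plan already define a comparator?** The secondary aim mentions controls and an untreated wrist vein and uses a paired McNemar test, which could point to the other arm. The same text compares with the baseline state and allows for veins that were adequate on the preliminary measurement to fall below the cut-off. That is a pre-post comparison. No formula, test or sample size names the other arm, and the randomization code has nothing to allocate between.

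**5. Treated-minus-untreated change.** A shift common to both arms cancels, so the upper-tail error stays at 2.5%. The SD of the contrast is √(0.75² + s₂² − 2·r·0.75·s₂).

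For s₂, take 0.5 × √(2(1 − ρ)). With ρ = 0.5 this is 0.50 mm. Reaching 0.75 mm would need ρ = −0.125, so 0.75 mm is the cautious case. Power at 0.25 mm:

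| s₂ (mm) | r | SD (mm) | 90 pairs | 80 pairs |
|---|---|---|---|---|
| 0.50 | 0 | 0.901 | 74% | 69% |
| 0.50 | 0.5 | 0.661 | 94% | 92% |
| 0.75 | 0 | 1.061 | 60% | 55% |
| 0.75 | 0.5 | 0.750 | 88% | 84% |

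At 0.50 mm the lowest power in these cases is 99.3% with 90 pairs and 98.6% with 80.

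**The case against.** A single-arm pre-post primary is a recognised choice for early work. The Background presents this as the first proposal of dilation before surgery, and the primary matches the hypothesis as worded. That stands, and it is why the primary should stay. The gap lies between that contrast and the causal Objective and Specific Aim.

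The controls in the secondary aim may well mean the other arm. That is plausible, but the text also points to baseline. Even on the favourable reading, it covers proportions only and leaves the mean change uncontrolled.

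The Doppler section is the dedicated measurement text and says explicitly that both arms are scanned at baseline. The Protocol paragraph is a summary and does not exclude the other arm. The conflict is therefore mild, but the availability of untreated-arm data rests on the Doppler section being followed.

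The most substantial objection is that the other arm is an imperfect control. The exclusion for earlier vascular surgery can be read as applying to the non-dominant arm only, and the 1.0 to 3.0 mm diameter screen names no arm. If screening applies to the treated arm alone, regression to the mean would not be shared. For an assumed 0.10 mm shift in the treated arm only (s₂ = 0.5 mm, r = 0.5, 90 pairs), the contrast gives a false positive 29% of the time, against 24% for the pre-post test. This limits what the contrast can show and supports giving it a supportive role. It does not rescue causal inference from the pre-post test.

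**Conclusion.** The concern holds and should be fixed. The primary is valid for change from baseline and Table 2 is correctly sized, but the test cannot separate a device effect from background change. At n = 90 and SD 0.75 mm, an assumed upward drift of 0.10 mm raises the chance of a spurious significant increase from 2.5% to 24%. The documents give neither the size nor the direction of drift, so these figures show sensitivity and do not predict bias. The contrast with the untreated arm removes change common to both arms and nothing more.

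**What to change.** 1. Keep the pre-post change as primary with Table 2 unchanged. Report it with a 95% confidence interval and describe it as change from baseline only.
2. Prespecify, as the key supportive analysis for attribution, the within-patient difference in change: (Post − Pre, treated arm) − (Post − Pre, untreated arm). Name one of the two measurement locations. Use a paired t-test or a mixed model with an arm-by-visit term, and give a 95% confidence interval. Include patients with a measurable vein in both arms and report how many are excluded.
3. Reconcile the Doppler and Protocol paragraphs so that both arms are scanned at baseline and follow-up.
4. State whether the controls in the secondary aim are the untreated arms, and what the randomization code assigns. If a separate control group is intended, use it for attribution.
5. If no comparator is used, limit the conclusions to change from baseline.

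**Cost.** Text only if the Doppler section stands; otherwise one additional arm is scanned at each visit. Arm is fixed by dominance and not randomised, so the contrast supports attribution without proving it. It partly subtracts any systemic effect of the device. Its power at 0.25 mm could be as low as 60% with 90 pairs, or 55% with 80, under the most cautious assumptions above.

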We would consider calculated effect sizes of 0.25-1.0 mm to be clinically meaningful changes that would increase the numbers of patients with vein diameters that meet commonly accepted thresholds for surgical suitability (normally 2.5-3.0 mm). Sample size calculations for a variety of effects are presented in table 1 (below), based on paired t-tests with alpha error of 0.05, standard deviation of the effect size of 0.75 mm, for power of 80% and 90%.

| Table 2 . Sample size required tocompare vein size before and aftertreatment | | | | |
|---|-------|-------|--|--|
| Effect size mm) | 80% | 90% | | |
| | power | power | | |
| 0.25 | 73 | 97 | | |
| 0.50 | 21 | 27 | | |
| 0.75 | 11 | 14 | | |
| 1.00 | 8 | 9 | | |
| 1.25 | 6 | 7 | | |
| 1.50 | 5 | 6 | | |

A secondary aim will be to compare the proportions of treated patients who achieve 3month vein diameters of 2.5 mm and 3.0 mm, to proportions achieved among controls. Given a normal distribution around a mean vein diameter of 1.8 mm with a standard deviation of 0.5 mm, the probability of an untreated wrist vein exceeding 2.5 mm (or 3.0 mm) would be 8.1% and 0.8%, respectively. Given that the standard deviation of the diameter of treated veins is at least 0.75, then the observed probabilities of a treated vein exceeding either 2.5 mm or 3.0 mm can be calculated, and is shown in the table below, any of which could be shown to be a significantly different proportion from the baseline state. The sample sizes required to demonstrate a difference in proportions were calculated using a McNemar test of paired proportions, with the very conservative assumption that 10% of veins that are adequate on preliminary measurement may fall below the cut-off value, due to variation in measurements.

| Table 3. Sample sizes required to demonstrated increased proportions of | | | | | | |
|---|---------|-----------------|-------|---------|-----------------|-------|
| surgically adequate veins | | | | | | |
| Effect | % veins | Required sample | | %veins | Required sample | |
| size | >2.5 mm | 80% | 90% | >3.0 mm | 80% | 90% |
| | | power | power | | power | power |
| 0.25 | 27.4 | 42 | 55 | 10.2 | 83 | 110 |
| 0.50 | 39.6 | 24 | 31 | 17.6 | 45 | 59 |
| 0.75 | 47.5 | 19 | 24 | 27.4 | 28 | 36 |
| 1.00 | 68.8 | 11 | 14 | 39.6 | 18 | 23 |
| 1.25 | 77.9 | 9 | 11 | 47.5 | 15 | 18 |
| 1.50 | 85.3 | 8 | 9 | 68.8 | 9 | 11 |

We intend to study 90 patients, and anticipate effects which should be more than adequate for these purposes.

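### Table 3's 3.0 mm column assumes baseline wrist veins that eligibility excludes, two printed percentages do not follow from the SD of 0.75 mm, and a rise above either threshold can occur without mean dilation (minor, secondary aim)

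*Combined protocol and SAP*

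**What the plan says.** The secondary aim in STATISTICAL ANALYSES compares the proportions of treated patients reaching 2.5 mm and 3.0 mm at three months "to proportions achieved among controls". The sizing text starts from a normal distribution with mean 1.8 mm and SD 0.5 mm, so that "the probability of an untreated wrist vein exceeding 2.5 mm (or 3.0 mm) would be 8.1% and 0.8%, respectively". It continues: "Given that the standard deviation of the diameter of treated veins is at least 0.75", and tabulates the resulting proportions for effects of 0.25 to 1.50 mm, "any of which could be shown to be a significantly different proportion from the baseline state". Table 3 uses a McNemar test and assumes that "10% of veins that are adequate on preliminary measurement may fall below the cut-off value".

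Under SUBJECTS, "Patients will have a preliminary evaluation of their cephalic vein, measured 5 cm proximal to the styloid process of the radius"; the antecubital fossa is a second site. Patients are excluded if no superficial vein of at least 1.0 mm is found, and "also if a superficial vein of more than 3.0 mm is present in this lower arm location".

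The Doppler paragraph of METHODOLOGY places the baseline scan at consent and covers both arms. The Protocol paragraph names only the nondominant arm for the Doppler after consent. Table 1 lists one baseline Doppler. No section says whether the screening scan is the baseline scan, and Outcomes names no analysis site.

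**The concern.** The 0.8% describes an unselected population, whereas the trial enrols a selected one. On the screening scan no enrolled wrist vein exceeds 3.0 mm, so the 10% fall-back allowance at that threshold applies to nobody.

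The more important matter is interpretation. The trial's hypothesis is that use of the device enlarges veins, "resulting in increased absolute vein diameters at three months when compared to baseline values". A significant before-after rise in veins above a surgical threshold would readily be taken as support. A proportion above a cut-off in the upper tail also rises when the spread widens, and the plan itself assumes a wider spread after treatment.

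**Working it through.** **Inputs.** All are from STATISTICAL ANALYSES unless noted: baseline mean 1.8 mm and SD 0.5 mm; treated-vein SD 0.75 mm; SD of change 0.75 mm; fall-back 10%; alpha 0.05 (stated for the t-test table; two-sided reproduces Table 3); N = 90. Limits of 1.0 and 3.0 mm come from SUBJECTS.

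**1. Reproducing the plan.** P(Z > (2.5 − 1.8)/0.5 = 1.4) = 8.1% and P(Z > 2.4) = 0.8%, as printed. For Table 3, let p0 be the baseline and p1 the follow-up proportion. Then p_down = 0.1·p0, p_up = p1 − 0.9·p0, ψ = p_up + p_down, d = p_up − p_down, and

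n = [1.960·√ψ + z_power·√(ψ − d²)]² / d².

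For 3.0 mm and effect 0.25 mm: p0 = 0.008 and p1 = 0.102 give p_down = 0.0008, p_up = 0.0948, ψ = 0.0956, d = 0.0940. At 80% power, (1.960 × 0.3092 + 0.8416 × 0.2946)² / 0.008836 = 82.5, so 83; at 90%, 110. The full column is 83/110, 45/59, 28/36, 18/23, 15/19, 9/11. Eleven of 12 cells match exactly; the other is 19 against a printed 18 (18.03 before rounding up). The 2.5 mm column matches in all 12 cells. The 0.8% and the fall-back are therefore real inputs.

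**2. Applying eligibility.** With p0 = 0, ψ = d = 0.102 in the first row, and (1.960 × 0.3194 + 0.8416 × 0.3027)² / 0.010404 = 74.6, so 75. With the printed percentages the column becomes 75/99, 43/56, 27/34, 18/23, 14/18, 9/11. In patients, the 0.8% is 0.008 × 90 = 0.7, and the fall-back is 0.07.

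**3. Checking the printed percentages.** With SD 0.75 mm, P(Z > (2.5 − 1.8 − 0.75)/0.75 = −0.067) = 52.7%, printed as 47.5%. P(Z > (2.5 − 1.8 − 1.00)/0.75 = −0.40) = 65.5%, printed as 68.8%. The same z values recur in the 3.0 mm column at effects 1.25 and 1.50 mm, so both errors appear twice. At 2.5 mm the 1.25 mm row is 76.8% (printed 77.9%). The 1.50 mm row is 85.7% (printed 85.3%). Neither changes its sample size.

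**4. A rise without a mean increase.** If the mean stays at 1.8 mm and the SD goes from 0.5 to 0.75 mm, the proportion above 3.0 mm goes from 0.8% to P(Z > 1.6) = 5.5%, and above 2.5 mm from 8.1% to P(Z > 0.933) = 17.5%. The correlation follows from the plan's SDs: 0.75² = 0.5² + 0.75² − 2r(0.5)(0.75), so r = 1/3. With no downward crossings, six upward crossings reach p = 0.031 on the exact test, and four suffice for the uncorrected chi-square (4 > 3.84).

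The table gives the percentage of simulated trials (N = 90, mean change within 0.06 mm of zero) with a significant upward result, exact/uncorrected, against a nominal 2.5%:

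| Threshold, post SD | No limits | 3.0 mm ceiling | 1.0 mm floor and ceiling |
|---|---|---|---|
| 3.0 mm, 0.75 | 23/47 | 35/71 | 39/75 |
| 3.0 mm, 0.65 (r = 0.5 assumed) | 3/18 | 6/29 | 7/33 |
| 3.0 mm, 0.50 | 0.0/at most 0.8 | 0.0/at most 0.8 | 0.0/at most 0.8 |
| 2.5 mm, 0.75 | 45/54 | 51/60 | 51/61 |

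With both limits and SD 0.75 mm, about 5 of 90 veins are newly above 3.0 mm and none can cross downward. If baseline is a separate scan (assumed measurement error SD 0.1 to 0.3 mm, ceiling alone), the 3.0 mm rates fall from 30/62 to 24/50, close to the figures without limits.

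**The case against.** The strongest reply is that a reader might infer that the eligibility ceiling itself manufactures significant results. The documents do not support that. With equal spread the 3.0 mm rate is 0.0% exact and below 1% uncorrected, under the nominal level. With SD 0.75 mm it is already 23%/47% with no ceiling, and the 2.5 mm threshold, which the ceiling barely touches, does worse. Spread is the driver and the ceiling adds to it at 3.0 mm. This stands.

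It also stands that pairing SD 0.75 mm with no mean change is a constructed scenario: the plan uses that SD with positive effects and says nothing about readings becoming noisier. If the extra spread reflects varied true response, the veins newly above a threshold did enlarge. Table 3 is about surgical adequacy, whereas dilation is the primary mean change. In the zero-change scenario with SD 0.75 mm, a significant threshold result coincides with a significant positive paired t-test in only about 1% to 3% of trials, so the primary analysis already guards a careful reader.

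Finally, 0.8% is given for an untreated vein, and the aim names controls. For an unscreened comparison arm, 0.8% could be right. That does not rescue Table 3, whose text refers to the baseline state and to veins adequate on a preliminary measurement. It is a reason to keep the 0% conditional.

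**Conclusion.** Three things hold, all minor because the aim is secondary.

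- The 3.0 mm column conflicts with eligibility. The 0% baseline requires that the screening scan is the baseline, that the wrist is the analysis site (the ceiling does not clearly apply at the antecubital fossa), and that the threshold means more than 3.0 mm. If it means at least 3.0 mm, veins recorded at exactly 3.0 mm would count at baseline.
- The printed 47.5% and 68.8% are wrong for SD 0.75 mm, in both threshold columns.
- A before-after rise at either threshold is not by itself evidence of dilation. The size of this problem runs from nothing at equal spread to the rates shown for SD 0.75 mm.

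A reader might also infer that the sample size is undermined, that McNemar's test is invalid, or that the primary outcome is biased. None follows. At a 0.25 mm effect, 90 patients cover 80% power but not 90% under either baseline (83/110 or 75/99). McNemar still validly tests the change in proportion. The paired comparison of means is not affected by the one-way crossing.

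**What to change.** 1. Correct Table 3. With a 0% baseline and normal tails from SD 0.75 mm (52.7% and 65.5% in the last two rows), the 3.0 mm column is 75/99, 43/56, 27/34, 18/23, 13/16, 10/12. In the 2.5 mm column the 0.75 and 1.00 mm rows become 52.7% with 16/20 and 65.5% with 12/15, and the 1.25 mm percentage becomes 76.8%. State the analysis site, which scan is the baseline, and whether the threshold means at least or more than.
2. Report the number newly reaching 2.5 and 3.0 mm with exact confidence intervals, as a description of surgical adequacy, beside the mean change (for example 5 of 90 = 5.6%, 95% CI 1.8% to 12.5%). State that a significant before-after McNemar result at either threshold is not read as dilation unless the paired mean change supports it.
3. Define controls or drop the word. First reconcile the Doppler and Protocol paragraphs on whether both arms are scanned. If they are, the contralateral arm can serve as a supportive comparison with its own power stated.

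Items 1 and 2 cost only wording. Item 3 costs power. An exact McNemar test between arms, among patients with both wrist veins at or below the threshold at baseline, has about 15% to 16% power at 3.0 mm and 26% to 27% at 2.5 mm for a 0.25 mm effect, and about 69% and 85% for 0.5 mm. These figures assume baseline between-arm correlations of 0.3 to 0.8 and an unscreened contralateral arm; about 11 to 13 of 90 patients drop out of the 2.5 mm comparison. It also assumes no device effect on the other arm. Nor does it remove the spread problem: if only the treated arm widens (0.75 against 0.5 mm), upward results without mean dilation still appear in about 24% of trials at 3.0 mm and 42% to 43% at 2.5 mm.
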